1.0 Study Summary

Study Title	Accuracy of the NICCI™ monitor in providing beat-to-beat non-invasive blood pressure readings in children and adolescents
Study Design	Prospective, non-blinded comparative study
Primary Objective	The primary objective of this study is to compare the blood pressure reading (systolic, diastolic, and mean) from an arterial cannula with the readings obtained from the non-invasive continuous blood pressure monitoring, NICCI™
Secondary Objective(s)	None
Research Intervention(s)/ Investigational Agent(s)	Measuring beat-to-beat blood pressure non-invasively with the NICCI™ monitor. There will be no change in anesthetic management or use of investigational pharmacological agents.
IND/IDE #	Not applicable
Study population	Patients who are scheduled for elective, urgent or emergent surgery
Sample size	150 (50 in each of 3 weight groups 10-20 kg, 20-40, and \geq 40 kg)
Study duration for individual participants	Duration of the surgical procedure (2-10 hours)
Study Specific Abbreviations/ Definitions	BP = blood pressure sBP = systolic blood pressure dBP = diastolic blood pressure MAP = mean arterial pressure NIBP = non-invasive blood pressure IBP = intra-arterial blood pressure

2.0 Objectives

2.1 The primary objective of this study is to compare blood pressure (BP) readings obtained from an invasive arterial cannula and a non-invasive continuous BP device. The hypothesis is that this novel non-invasive device will provide an accurate and continuous estimation of BP.

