4.0 Study Endpoints

4.1 The primary study endpoint is to compare the BP readings from the non-invasive NICCI device with those obtained from an arterial cannula.

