6.0 Procedures Involved*

6.1 This is a prospective study that will compare the blood pressure readings from an arterial cannula with those obtained non-invasively by the NICCI device. The study will enroll 50 patients into each of three weight ranges: 10-20 kg, 20-40 kg, and 40-80 kg.

6.2 The study cohort will include patients requiring anesthetic care and in whom an indwelling arterial cannula will be placed for the surgical procedure. The arterial cannula will not be placed for the purpose of the study. The NICCI™ monitor will be attached to the patient and simultaneous readings from the NICCI™ monitor and the invasive arterial cannula will be downloaded every minute into a laptop computer for later analysis.

6.3 Exclusion criteria:

- Patients with history of a peripheral neurologic or neuropathic disorder
- Patients in whom the upper extremity cannot be used for blood pressure monitoring
- Patients in whom an invasive arterial cannula cannot be placed
- Patients with vascular implants at the sites of non-invasive blood pressure measurement (fingers and upper arm of the examined arm)
- Edematous patients

6.4 There are no foreseeable risks associated with the use of NICCI™ device.

6.5 The data (BP readings) will be downloaded into a bedside NCH laptop in the operating room and stored on our password-secured server.

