9.0 Study Timelines*

- 9.1 An individual study subject's participation in the study should last 2-10 hours depending on the duration of the surgical procedure.
- 9.2 All study subjects should be enrolled within 1 year of the start of the study.
- 9.3 The study data will be analyzed, a manuscript written, and the study completed within 18 months of the start of the study.

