17.0 Data Management* and Confidentiality

17.1 Statistical analysis and data presentation will include a calculation of the absolute difference of the sBP, dBP and MAP values of the two devices. To avoid biasing the data, the absolute not directional difference will be used. For example, if the reading from NICCI™ device was 10 mmHg above or below the reading from the AL, a value of 10 mmHg was used, not -10 or +10 mmHg. Additionally, a determination will be made of the percentage of values from the NICCI™ device that are \leq 5 mmHg and more than 10 mmHg from the IBP values. A Pearson correlation coefficient will be calculated comparing the sBP, dBP and MAP values between the arterial cannula and the NICCI™ device. A Bland-Altman analysis with multiple measurements per subject will be performed to determine the bias and 95% level of agreement for the three groups.

17.2 De-identified data will be shared with the manufacturer of the monitor, Getinge. They will be assisting with data analysis, as well as, using the data for a 510(K) submission to the FDA.

17.3 Research records will be stored in a locked cabinet and password protected computer. Only certified research personnel will be given access to identifiable subject information

17.4 Following publication of study results, research records will be stored for a period of 5 years and then will be destroyed by placing in a secure shredding bin.

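### Section 2.1 hypothesises accuracy, but the plan names no deciding output, confidence interval or acceptance limit, and 17.1 wrongly treats dropping the sign of the difference as protection against bias

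*Combined protocol and SAP*

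**What the plan says.** Section 2.1 sets a hypothesis that can be right or wrong: "The hypothesis is that this novel non-invasive device will provide an accurate and continuous estimation of BP". Section 4.1 gives the primary endpoint: "The primary study endpoint is to compare the BP readings from the non-invasive NICCI device with those obtained from an arterial cannula". It names no variable, summary measure or criterion.

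Section 17.1 is the only analysis text. For systolic, diastolic and mean pressure it plans:

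- the absolute difference, with this reason: "To avoid biasing the data, the absolute not directional difference will be used". Its example confirms that the sign is discarded: "a value of 10 mmHg was used, not -10 or +10 mmHg";
- the percentage of NICCI values within 5 mmHg of the arterial value and the percentage more than 10 mmHg away, with no required percentage;
- a Pearson correlation, with no threshold;
- agreement by weight group: "A Bland-Altman analysis with multiple measurements per subject will be performed to determine the bias and 95% level of agreement for the three groups".

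No output is called primary or deciding, and no confidence interval is planned. The 95% level of agreement describes the spread of differences; it is not a confidence interval. Section 17.2 adds that the manufacturer will receive the data: "They will be assisting with data analysis, as well as, using the data for a 510(K) submission to the FDA".

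**The concern.** A hypothesis of accuracy needs a statement of what would count against it. Here there are four kinds of output, three pressures and three weight groups, with no rule for which of them decides or what value is good enough. Followed exactly, the plan can describe agreement but cannot soundly support or reject the word accurate.

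The reason given for absolute differences makes this worse, because it is wrong. Bias in a method comparison is the mean of the signed difference. Taking absolute values does not remove bias; it removes the information that shows it. A reader who follows that sentence could take the absolute difference as the main result, or even carry it into the Bland-Altman analysis. A device that reads consistently high would then look the same as one that reads consistently low.

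**Working it through.** **The plan's own figure.** The sample size is 150, as 3 × 50 (sections 1.0 and 6.1). No SD, margin, target precision, alpha or power is given, so it cannot be re-derived, and no acceptance limit can be inferred from it.

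**What absolute differences can show.** The SDs and biases are assumptions, since the documents give none. Let the signed difference d be normal with bias b and SD s, and let Φ be the standard normal distribution function.

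- P(|d| ≤ c) = Φ((c − b)/s) − Φ((−c − b)/s)
- Mean |d| = s·√(2/π)·exp(−b²/(2s²)) + b·(1 − 2Φ(−b/s))
- Limits of agreement = b ± 1.96·s

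For b = 0, s = 8:

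- within 5: 2Φ(0.625) − 1 = 0.468
- beyond 10: 2(1 − Φ(1.25)) = 0.211
- mean |d| = 8 × 0.798 = 6.38

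For b = 5, s = 6:

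- within 5: Φ(0) − Φ(−1.667) = 0.500 − 0.048 = 0.452
- beyond 10: 1 − [Φ(0.833) − Φ(−2.5)] = 0.209
- mean |d| = 3.38 + 2.98 = 6.36

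For b = −5 the absolute results are identical by symmetry.

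| Device | Within 5 mmHg | Beyond 10 mmHg | Mean absolute difference | Signed limits of agreement |
|---|---|---|---|---|
| bias 0, SD 8 | 46.8% | 21.1% | 6.38 | −15.7 to 15.7 |
| bias +5, SD 6 | 45.2% | 20.9% | 6.36 | −6.8 to 16.8 |
| bias −5, SD 6 | 45.2% | 20.9% | 6.36 | −16.8 to 6.8 |

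The last two rows cannot be told apart by any absolute-difference output. The first differs from them by 46.8 − 45.2 = 1.6 percentage points within 5 mmHg and by 0.2 points beyond 10. Pearson correlation does not help, because adding a constant to one device leaves it unchanged. The signed limits separate all three. If the Bland-Altman analysis were run on absolute differences, its bias would be the mean absolute difference, about 6.4 mmHg in every row.

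**Precision available at 50 per group.** Section 6.2 says that "simultaneous readings from the NICCI™ monitor and the invasive arterial cannula will be downloaded every minute into a laptop computer for later analysis", and section 9.1 says that "participation in the study should last 2-10 hours depending on the duration of the surgical procedure". That is 2 × 60 = 120 to 10 × 60 = 600 readings per child. Take n = 50, t(49) = 2.01 and m = 120. Split the variance into a between-child part vb = share × SD² and a within-child part vw = (1 − share) × SD².

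- Half-width of the 95% CI for bias = t·√((vb + vw/m)/n)
- Half-width for each limit = 1.96·√(var(bias) + 1.96²·var(SDtotal)), where var(bias) = (vb + vw/m)/n and var(SDtotal) = [2(vb + vw/m)²/(n − 1) + (1 − 1/m)²·2vw²/(n(m − 1))]/(4·SD²)

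For SD 8 and a 30% share, vb = 19.2 and vw = 44.8. The bias half-width is 2.01 × √((19.2 + 0.37)/50) = 1.26, and the limit half-width is 1.56. With one effective value per child, the bias half-width is 2.01 × √(64/50) = 2.27. The limit half-width is then 1.96 × √(1.28 + 3.84 × 0.653) = 3.82.

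| Assumed SD | Bias half-width (mmHg) | Half-width of each limit (mmHg) |
|---|---|---|
| 6 | 0.94 to 1.71 | 1.17 to 2.86 |
| 8 | 1.26 to 2.27 | 1.56 to 3.82 |
| 10 | 1.57 to 2.84 | 1.95 to 4.77 |

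Each range runs from a 30% between-child share to one effective value per child. Raising m from 120 to 600 changes the SD 8 bias half-width by 0.01 or less.

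**The case against.** The strongest reply is that this is a descriptive method-comparison study. The objective and the endpoint are both worded as a comparison, and a Bland-Altman analysis with multiple measurements per subject is the standard tool. Much of this stands. A descriptive aim is coherent, but then 2.1 should not state a hypothesis of accuracy, and intervals are still needed to show how precise the description is.

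Four stronger readings are tempting, and the documents do not support them.

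- *The plan would miss bias or poor agreement.* It would not, provided the Bland-Altman analysis uses signed differences. Its stated purpose of determining bias points that way, although 17.1 does not say so.
- *The absolute difference is the chosen main result.* It comes first in 17.1, but nothing there ranks the outputs.
- *Absolute differences can never distinguish a biased device from an unbiased one.* That is exact only for the direction. The SDs above were chosen to give a close match. With SD 10 and bias 0, 38.3% of readings fall within 5 mmHg; with bias 7 and SD 6.60 it is 34.6%, at the same mean absolute difference.
- *The manufacturer will set the standard after seeing the data, or the analysis will ignore clustering.* Section 17.2 says only that the manufacturer assists with analysis and uses the data for a submission. Who sets any standard, and when, is not stated. Section 17.1 explicitly provides for multiple measurements per subject.

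**Conclusion.** The point holds as a gap between the hypothesis and the analysis, together with one wrong methodological statement. No result is defined as failing 2.1, no output decides, and no confidence interval is planned. The reason given in 17.1 for absolute differences is incorrect: the direction of bias is lost entirely, and in the example a 5 mmHg bias moves the reported percentages by less than 2 points.

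The example rests on normal differences with assumed SDs of 8 and 6 mmHg. The precision figures rest on assumed SDs and variance shares; at SD 8 they are about 1.3 to 2.3 mmHg for the bias and 1.6 to 3.8 mmHg for each limit. Whether 50 per group is enough for a claim of accuracy cannot be judged, because the plan has no margin to judge it against. The gap in the text depends on none of these assumptions. The sponsor should correct it, and the analysis needed is already largely planned.

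**What to change.** 1. In 17.1, delete the statement that absolute differences avoid bias. In 4.1 and 17.1, make the signed difference (NICCI minus arterial) from the repeated-measures Bland-Altman analysis primary for systolic, diastolic and mean pressure in each weight group. Keep absolute differences, percentages and Pearson correlation as descriptive.
2. Report 95% confidence intervals for the bias and for each limit of agreement, accounting for repeated readings within child.
3. Reword 2.1 as estimation of agreement, and draw no pass/fail conclusion of accuracy.

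If the sponsor prefers to keep the hypothesis, a dated document should fix the maximum bias and limits and say which pressures and groups must meet them. It should be completed before first enrolment. The study is non-blinded and both readings are taken in the operating room, so investigators may see pairs from the first patient. If enrolment has begun, the document should state that the margins were set afterwards. The chosen margins should be checked against 50 per group.

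The cost is protocol wording and a little more analysis of data already planned, with no additional patients or measurements. The estimation route gives up a formal accuracy claim. The hypothesis route adds a short margin document and means that the study can fail.

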3.0 Background

3.1 BP is one of the most important parameters in several clinical settings. Particularly during the perioperative period, BP needs to be monitored repeatedly or even continuously to facilitate the best care for patients. This is done either intermittently using an oscillometric non-invasive blood pressure device (NIBP) or continuously by an invasive arterial line (IBP). A number of clinical studies show that both methods may have pitfalls and at times be inaccurate. Since the NIBP provides discontinuous pressure readings with the current recommendations for intraoperative monitoring stating that the BP should be monitored every 5 minutes, hemodynamic events may be missed or there may be a delay in recognition of alterations in BP. Therefore, during major intraoperative procedures in patients with co-morbid cardiac diseases or during procedures with significant blood loss, invasive arterial monitoring of BP is chosen with placement of an intra-arterial cannula. Although generally safe and effective, the placement of an intra-arterial cannula may be

PROTOCOL TITLE: Accuracy of the NICCI™ monitor

associated with complications including artery occlusion with distal ischemia, hematoma formation, blood loss due to unintended disconnection, infection or nerve damage with sensory disturbance. More importantly, arterial cannulation takes time and may at times be impossible. Therefore, a method that non-invasively allows the continuous measurement of BP would be clinically useful.

3.2 The NICCI, Pulsion/GETINGE uses novel technology to provide a continuous estimation of BP displayed as a waveform similar to that seen with an invasive arterial cannula (information attached). Infrared (IR) light, emitted from a Light Emitting Diode, is sent through the finger. The light is partly absorbed by the arterial blood, which is changing according to the heart activity (pulse). A light detector receives the remaining light on the other side of the finger and thus detects the continuous pulse signal. Counter pressure is exerted from the outside in such a way that the arterial wall is totally unloaded. This continuously changing outside pressure keeps the arterial blood volume constant at all times and directly corresponds to the arterial pressure. The intra-arterial pressure is therefore measured indirectly. To calibrate the continuous pulse-contour curve with the correct absolute blood pressure values, an automatic non-invasive blood pressure (NIBP) measurement is either performed on the patient's upper arm or provided by the user. This device is based on technology originally developed as the CNAP™ monitor which has been tested and validated by us previously in other IRB-approved trials.

23 Tobias JD, McKee, Herz D, Teich S, Sohner P, Rice J, Barry N, Michalsky M. Accuracy of the CNAP™ monitor, a non-invasive continuous blood pressure device, in providing beat-to-beat blood pressure measurements during bariatric surgery in severely obese adolescents and young adults. *J Anesth* 2014;28:861-865.

4.0 Study Endpoints

4.1 The primary study endpoint is to compare the BP readings from the non-invasive NICCI device with those obtained from an arterial cannula.

5.0 Study Intervention/Investigational Agent

5.1 The only novel intervention is the use of the NICCI device to monitor blood pressure. No change in the anesthetic technique will be required during the study. The study will include only patients scheduled for a surgical procedure that requires invasive monitoring of arterial blood pressure (placement of an arterial cannula).

6.0 Procedures Involved*

6.1 This is a prospective study that will compare the blood pressure readings from an arterial cannula with those obtained non-invasively by the NICCI device. The study will enroll 50 patients into each of three weight ranges: 10-20 kg, 20-40 kg, and 40-80 kg.

6.2 The study cohort will include patients requiring anesthetic care and in whom an indwelling arterial cannula will be placed for the surgical procedure. The arterial cannula will not be placed for the purpose of the study. The NICCI™ monitor will be attached to the patient and simultaneous readings from the NICCI™ monitor and the invasive arterial cannula will be downloaded every minute into a laptop computer for later analysis.

6.3 Exclusion criteria:

- Patients with history of a peripheral neurologic or neuropathic disorder
- Patients in whom the upper extremity cannot be used for blood pressure monitoring
- Patients in whom an invasive arterial cannula cannot be placed
- Patients with vascular implants at the sites of non-invasive blood pressure measurement (fingers and upper arm of the examined arm)
- Edematous patients

6.4 There are no foreseeable risks associated with the use of NICCI™ device.

6.5 The data (BP readings) will be downloaded into a bedside NCH laptop in the operating room and stored on our password-secured server.

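### Calibration times and values are not committed to the data set and the analysis ignores them, so the pooled agreement cannot show how much comes from tracking between calibrations

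*Combined protocol and SAP*

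**What the plan says.** Section 3.2 describes a finger sensor that follows the pulse continuously, and then explains where the absolute level comes from: "To calibrate the continuous pulse-contour curve with the correct absolute blood pressure values, an automatic non-invasive blood pressure (NIBP) measurement is either performed" on the "upper arm or provided by the user". It does not say how often this happens or which route the study will use.

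Section 3.1 gives the reason for wanting the device. It cites a recommendation that "the BP should be monitored every 5 minutes" and says that with intermittent readings "hemodynamic events may be missed or there may be a delay in recognition of alterations in BP". Section 2.1 states: "The hypothesis is that this novel non-invasive device will provide an accurate and continuous estimation of BP".

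On data capture, section 6.2 says that "simultaneous readings from the NICCI™ monitor and the invasive arterial cannula will be downloaded every minute into a laptop computer for later analysis". Calibration times and calibrating values are not mentioned.

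Section 17.1 plans four outputs for sBP, dBP and MAP: the unsigned difference, the percentages within 5 mmHg and beyond 10 mmHg, Pearson's r on the levels, and a repeated-measures Bland-Altman analysis for the three groups. None uses time since calibration, change since calibration, or the cuff value.

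**The concern.** A NICCI reading has two ingredients: a level taken from the last calibration, and the movement that the finger sensor has added since. Only the second is new relative to the intermittent cuff. Soon after a calibration, agreement in mmHg mainly reflects how good the calibrating value was. Late in the interval it depends on tracking. The planned outputs average over both, and the Bland-Altman method allows for clustering by child but not for calibration cycles.

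Two things are at stake. First, if calibration is frequent or pressure is stable, good pooled figures are weak evidence for the continuous part of the hypothesis. Second, pooled limits depend on the calibration schedule that happened to be used. Unless it is reported, a reader cannot carry them over to another schedule. Section 17.2 says the data will also be used in a 510(K) submission, and calibration events not saved in the operating room may not be recoverable later.

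**Working it through.** The documents give no figure to reproduce here. The only planning number is 150 = 3 × 50, and this point does not depend on it. Every numerical input below is an assumption.

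**Check 1: a display that holds the last cuff value.** Assume for MAP a within-child SD of 10 mmHg, a between-child SD of 8, cuff error SD 5, and autocorrelation exp(−k/τ) at k minutes with τ from 20 to 80 min. Calibration occurs every L minutes.

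- Error variance k minutes after calibration: 25 + 2 × 100 × (1 − exp(−k/τ)).
- Pooled limits: ±1.96 × √(mean of that variance over k = 0 to L − 1).
- r = (64 + 100 × mean of exp(−k/τ)) / √(189 × 164), where 164 = 64 + 100 and 189 = 164 + 25.
- Perfect tracking from the same cuff leaves only the cuff error: limits ±1.96 × 5 = ±9.8, r = √(164/189) = 0.93, 68% within 5 mmHg, about 5% beyond 10 mmHg.

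Worked case, L = 5 and τ = 20: the mean of exp(−k/τ) is 0.907. The variance is 25 + 200 × 0.093 = 43.6, the limits are ±1.96 × 6.60 = ±12.9, and r = 154.7/176.1 = 0.88.

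| Held value, interval | r | Within 5 mmHg | Beyond 10 mmHg | Limits (mmHg) |
|---|---|---|---|---|
| 5 min | 0.88-0.92 | 56-64% | 7-13% | ±10.7 to 12.9 |
| 15 min | 0.77-0.88 | 45-57% | 12-25% | ±12.6 to 17.6 |
| 30 min | 0.67-0.84 | 38-51% | 18-34% | ±14.8 to 21.4 |
| 60 min | 0.55-0.77 | 33-44% | 26-41% | ±18 to 25 |
| Perfect tracking | 0.93 | 68% | 5% | ±9.8 |

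With more volatile pressure (τ = 10), the held value at 5 min falls to 51% within 5 mmHg and limits of about ±15.

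**Check 2: against a tracking device that is not perfect.** This was a simulation of 2,000 children with 240 minutes each: between-child SD 10, within-child SD 6, 8 or 10, τ 10, 20 or 40 min, cuff error SD 4 plus a per-child offset of SD 3. The tracking device follows true pressure with noise SD 4, so its limits should be 1.96 × √(16 + 9 + 16) = ±12.5; the simulation gave ±12.5 to 12.6. The held value had the smaller mean absolute difference in 6 of 9 scenarios at 5 min, 1 of 9 at 15 min and 0 of 9 at 30 min. With calibration times available, the slope of device change on arterial change since calibration was 0.00 for the held value and 0.99-1.01 for the tracking device in all 27 scenarios.

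**Check 3: pooled against end-of-interval limits.** Assume cuff error SD 5 and drift of 1 mmHg per root-minute. Pooled: 1.96 × √(25 + (L − 1)/2). Last minute: 1.96 × √(25 + (L − 1)).

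- L = 30: 1.96 × √39.5 = 12.3 against 1.96 × √54 = 14.4.
- L = 60: 1.96 × √54.5 = 14.5 against 1.96 × √84 = 18.0.

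**The case against.** The strongest reply is that the study has one objective, agreement of NICCI with the arterial line (sections 1.0 and 4.1), and lists no secondary objectives. Pooled agreement as the device is used is a legitimate quantity, and beating the cuff is background motivation, not a planned claim. This stands: a requirement that NICCI outperform a held cuff value would add a success criterion the study does not have. It does not remove the point, because section 2.1 also hypothesises that "this novel non-invasive device will provide an accurate and continuous estimation of BP".

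A reader might infer that good agreement could never be told apart from a frozen display. The figures do not support that: at 30 minutes or more the planned outputs separate clearly. Slow change in pressure is also not stated anywhere, and the cohort is restricted to procedures requiring arterial monitoring, which section 3.1 links to cardiac comorbidity or significant blood loss.

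A reader might also infer that the device does not track, or that cuff values will be thrown away. Section 3.2 describes continuous sensing at the finger. Section 6.2 does not say that nothing else is saved; it leaves calibration data unspecified.

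Finally, the calibration interval and the drift rate are not in the documents. Section 3.2 refers to attached device information that was not available for this review. The conclusion has to be conditional on both.

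**Conclusion.** The point holds in conditional form, as an inexpensive improvement and not a flaw that invalidates the study. As written, the plan can estimate overall agreement but cannot show how much of it comes from tracking between calibrations. With calibration every 5 minutes, a held value can come close to a perfect tracker on the planned outputs, and can score better than a noisy one. At longer intervals or with volatile pressure it does visibly worse. Without a stated interval or a log, a reader cannot tell which situation the results describe.

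The understatement of end-of-interval error is about 2 mmHg at 30 min and 3.5 mmHg at 60 min under the assumed drift. It arises only if error grows between calibrations. No change in sample size follows.

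**What to change.** In section 6.2, commit to saving the time, value and source (cuff or user-supplied) of every NICCI calibration.

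In section 17.1, add two analyses:

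1. Bias and limits of agreement by minutes since the last calibration, reported beside the pooled limits.
2. As a descriptive comparison and not a success criterion, the same planned outputs for the last calibrating NIBP value carried forward to the next calibration, against IBP.

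Report the calibration intervals observed, and limit any conclusion about continuous accuracy to them.

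The cost is three fields per calibration, a paragraph in 17.1 and some programming, with no extra patients, procedures or change in care. The downside is that limits at the end of an interval may be less favourable than the pooled ones, and the gain over the carried-forward cuff value may turn out to be small.
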